## Home Based Virtual Rehabilitation for upper extremity

**Title of Project:**

**Principal Investigator:**

**[name] PT PhD**

**Funding Source(s):**

**NIDILRR #90RE5021-01-00**

**NIH NICHD #1R15HD095403-01A1**

### 1. Purpose/Specific Aims

The overarching aim of this study is to provide a mechanism for patients to engage in progressive motor practice for a meaningful time period. We aim to improve on the positive outcomes found in our work on patients in the chronic phase and the pilot work being done on patients in the acute in-patient phase post stroke to determine whether we can further improve functional recovery using a home based system.

Aim 1: Evaluate compliance with Home-Based Virtually Simulated hand/arm gaming activities and two computer game groups, one with motivation enhanced (ME) simulations and one with non-enhanced (MnE) versions, as compared to compliance with Standard hand/arm home Exercises (HBSE). Hypothesis: Participants in the ME and MnE group will show significant compliance as compared to the control group (HBSE) and the ME group will be superior to the MnE group.

Primary Outcome Measures: For the HBVS group, 1) time on task will be measured by the daily computer file time stamp and 2) amount of moving time will be measured by the actual movement time recorded by the games. For the computer games groups 1) time on task will be measured by recording start and stop time of practice in a notebook and 2) amount of moving time will be measured by commercially available activity monitors.

Aim 2: Evaluate the effectiveness of home-based virtually simulated hand/arm gaming activities (HBVS) for individuals with stroke as compared to a program of standard hand/arm home exercises (HBSE). Hypothesis: Participants completing HBVS training will exhibit significantly improved clinical, kinematic and neurophysiological outcomes as compared to the control group (HBSE).

Primary Outcome Measures for Aim 2: Wolf Motor Function Test, Upper Extremity Fugl-Meyer Assessment of Sensorimotor Recovery after Stroke, Action Research Arm Test, Perception of System Questionnaire, the Stroke Impact Scale, Kinematics, Cortical mapping.

Aim 3: Evaluate the impact of the motivation enhancements designed into computer games to provide a more enjoyable training experience. Hypothesis: Enjoyment of the games will be a more valid predictor of compliance than personal factors.

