## **3. Research Design and Methods**

This study will be a single blind randomized controlled trial. Subjects will be blinded to the purpose of the study. All outcome measures will be performed by a therapist blinded to group assignment. A controlled trial will be utilized to determine the additive effect of presenting rehabilitation activities in a virtual environment as compared to standard upper extremity exercise. We will randomize subjects to treatment and control groups using a computerized random number generator.

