### ***3.1. Duration of Study***

Each subject will perform a pre-study evaluation, train using one of the protocols for three to twelve months, perform a post study evaluation as well as one and six month retention evaluations.

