### ***3.3 Sample Size Justification***

In this pilot study we will seek sufficient power to detect a clinically significant difference in the Wolf score changes in these two pre-planned, primary comparisons. To evaluate these effects of training, we will assume a power level of .8 and a significance level of 0.05. With presumed correlation among repeated measures of 0.1 and effect size of 0.3, we will need a sample size of 25 subjects in each of the three groups (HBVS, ME and MnE) to observe a significant effect for the first comparison (G\*Power, version 3.1.5). Although we will screen for patients with homogeneous impairments, by its nature stroke is an extremely variable condition. Due to possible subject attrition, we will use a total of 30 subjects in each of the two groups.

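### Aim 2 words the treated group as those completing HBVS training, and no as-randomised analysis set is stated, so the plan points to a completer-type comparison that can be biased

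*Protocol*

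**What the plan says.** Protocol Section 1 sets the Aim 2 objective as "Evaluate the effectiveness of home-based virtually simulated hand/arm gaming activities (HBVS) for individuals with stroke", compared with standard home exercise. The hypothesis that follows is narrower: "Participants completing HBVS training will exhibit significantly improved clinical, kinematic and neurophysiological outcomes as compared to the control group (HBSE"). Completing is not defined. For Aim 1 the protocol predicts that "Participants in the ME and MnE group will show significant compliance as compared to the control group (HBSE").

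Protocol Section 3 says "We will randomize subjects to treatment and control groups using a computerized random number generator". Under Section 3.1 subjects "train using one of the protocols for three to twelve months" and are then tested after training and at one and six months.

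Protocol Section 3.3 finds 25 per group and adds: "Due to possible subject attrition, we will use a total of 30 subjects in each of the two groups".

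Protocol Section 5 names the Wolf Motor Function Test (WMFT) as the Aim 2 primary outcome. The test is a repeated-measures ANOVA with Therapy Type (virtual simulation or standard exercise) between groups and four test occasions within subjects. The section gives no analysis set and no rule for missing tests.

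The SAP's effectiveness aim (its Aim 3) compares the enhanced with the unenhanced game group and has no HBSE arm, so it does not settle the population for the protocol's Aim 2.

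**The concern.** Randomisation protects a comparison of groups formed by randomisation. A group formed by who finishes months of home practice has no such protection if finishing is related to recovery.

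The documents give some reason to expect that relation. The randomisation paragraph in the SAP (Aim 1, Subjects) says that level of impairment may affect both compliance with training and measures of effectiveness. That is a possible common cause of finishing and of outcome. Training of up to a year, with tests to six months beyond it, leaves ample time to stop.

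Two features of the plan point towards completers: the hypothesis wording, and an ANOVA that in its conventional form uses only subjects with all four tests. No statement that subjects are analysed as randomised offsets them. At stake is the main clinical comparison, on the WMFT.

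**Working it through.** **1. The plan's own figure.** Protocol Section 3.3 asks for power 0.80 at alpha 0.05. Its other inputs are given as "With presumed correlation among repeated measures of 0.1 and effect size of 0.3". Take the effect size as Cohen's f, the G*Power convention, and use the repeated-measures ANOVA between-groups test with k groups, m measurements and N subjects in total:

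λ = f² × N × m / (1 + (m − 1)ρ), with k − 1 and N − k degrees of freedom.

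For k = 2, m = 2, N = 50: λ = 0.09 × 50 × 2 / 1.1 = 8.18, and power is 0.800. So 25 per group reproduces. Going from 25 to 30 implies attrition of 1 − 25/30 = 16.7%. No rate by arm is given.

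**2. Bias if only the game arm is filtered.** Assume no true effect. Completers are the top fraction c of a latent normal variable whose correlation with the outcome is r. Their mean is shifted by

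bias = r × φ(z) / c, with z = Φ⁻¹(c), in SD units.

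- c = 0.833: φ(z)/c = 0.300.
- c = 0.70: φ(z)/c = 0.497.

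The documents give neither r nor c. The value c = 0.833 borrows the attrition allowance; c = 0.70 is purely an assumption. Type I error comes from 4,000 simulated trials per cell (two-sided t test at 0.05, completers out of 30 against all 30 controls).

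| Non-completion | r | Bias (SD, towards games) | Type I error |
|---|---|---|---|
| 16.7% | 0.1 | 0.03 | 0.05 |
| 16.7% | 0.3 | 0.09 | 0.06 |
| 16.7% | 0.5 | 0.15 | 0.08 |
| 30% | 0.1 | 0.05 | 0.05 |
| 30% | 0.3 | 0.15 | 0.08 |
| 30% | 0.5 | 0.25 | 0.13 |

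At r = 0 there is no bias.

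**3. Bias if non-completers drop from both arms.** This is what a complete-case ANOVA does if those who stop training also miss tests. With completion c₁ in HBVS and c₀ in HBSE,

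bias = r × [φ(z₁)/c₁ − φ(z₀)/c₀].

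| Completion, HBVS / HBSE (assumed) | r = 0.1 | r = 0.3 | r = 0.5 |
|---|---|---|---|
| 83.3% / 83.3% | 0 | 0 | 0 |
| 90% / 70% | −0.03 | −0.09 | −0.15 |
| 85% / 60% | −0.04 | −0.11 | −0.19 |

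A negative value works against games.

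**4. Power when everyone is analysed as assigned.** Use the model in step 1 with 30 per group (N = 60), and assume that non-completers get no benefit, so f becomes 0.3 × c.

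| Completion | f | Power, 30 per group | Per group for 80% |
|---|---|---|---|
| 100% | 0.30 | 0.87 | 25 |
| 90% | 0.27 | 0.79 | 31 |
| 83.3% | 0.25 | 0.73 | 36 |
| 70% | 0.21 | 0.58 | 50 |

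For 83.3%: λ = 0.0625 × 60 × 2 / 1.1 = 6.82.

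**The case against.** A reader might infer that Aim 2 will test game-arm completers against the whole control arm and that the result is therefore biased in favour of games. The documents do not support that.

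- A hypothesis sentence is not an analysis rule. It does not say that the control group is kept whole, and completing may mean no more than receiving the training. The Aim 2 objective has no completer restriction, and the test in Section 5 is by Therapy Type with no filter on either arm.
- The allowance from 25 to 30 is neutral. It is equally ordinary under an as-randomised analysis, and it is the same for each group.
- Compliance in Aim 1 is time on task and moving time, which is dose of practice and not dropout. No completion rate by arm is predicted.
- The direction is open. Loss from both arms with poorer completion in HBSE biases against games.
- Sections 3.1 and 4.2 already plan the tests for every subject, and neither makes them conditional on practice.
- Part of the SAP was not available for review. Table 5 and the SAP's Aim 3 analysis are not in the text, so absence is judged on what could be read.

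All of this stands, and it rules out a claim of demonstrated bias towards games. It does not supply the missing rule. Completing remains the only description of who counts on the treated side, and the planned ANOVA does not by itself keep subjects who miss a test.

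**Conclusion.** The point holds as a defect in the stated population: completer wording on one side, no as-randomised rule to override it, and a test that conventionally loses incomplete cases. The comparison can be biased; that it will be is not shown.

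At the only non-completion rate the documents imply, the one-arm reading gives at most 0.15 SD towards games for r up to 0.5, with a type I error of about 8%. The larger figures, up to 0.25 SD and about 13%, need an assumed 30% non-completion. The two-arm reading runs from zero to about −0.19 SD. Because even the sign depends on a rule the plan does not give, the rule should be fixed before outcome data are seen.

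One related matter needs separate reconciliation. Section 3.3 speaks of three groups and then of two, and 25 per group reproduces only with two groups and two measurements, while Section 5 plans four tests.

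**What to change.** - In protocol Section 1, word the Aim 2 hypothesis as participants randomised to HBVS compared with participants randomised to HBSE.
- In protocol Section 5, state that all randomised subjects are analysed in their assigned arm whatever their practice time, using a mixed model for repeated measures that keeps subjects with incomplete tests.
- State that subjects who stop training are still invited to the post-training, one-month and six-month tests already planned for all subjects.
- Report any completer comparison only as supportive, with one predefined completion rule applied to both arms.

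The cost is wording in two sections and attendance of subjects who stop training at visits already in the schedule. The real price is power: the as-randomised effect may be smaller than the effect among completers. If 16.7% get no benefit, power with 30 per group is about 73%, and 36 per group would be needed for 80%. The sponsor should either accept and state that or revisit the sample size.

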## **2. Background and Significance**

Studies have shown that sustained hand rehabilitation training is important for continuous improvement and maintenance of function following a stroke. It is unimaginably difficult to pursue education, employment and community participation without being able to independently use one's hands. The primary goal of this study is to test an exciting new technology that can be easily used in the home for long-term hand and upper extremity training. Recovery of hand function post brain injury is particularly recalcitrant to currently available interventions. To date, the best efforts of groups studying traditionally presented as well as technology-based therapeutic interventions for the hemiplegic hand and arm have produced measurable changes in motor function and motor control but fall far short of major reductions in disability.

If the amount of therapy is critical to rehabilitation, our current institutional limitations undermine the probabilities for successful outcomes. After discharge from the inpatient stay, access to rehabilitation therapy can be difficult for some patients. This is due in part to inadequate insurance, lack of transportation, and the patient's dependence on their caregiver. Having access to long-term rehabilitation training anywhere and at any time is necessary for sub-acute and chronic patients to continuously improve their functional abilities.

Innovative telerehabilitation systems have been developed using information and communication technologies to provide rehabilitation services at a distance. Many studies have developed video-game driven systems from commercially available gaming consoles such as Wii and Microsoft Kinect [1]. Other groups have examined the use of custom-made tele-rehabilitation systems [2, 3]. These systems do not address hand rehabilitation. There is a vital need to explore intensive home-based upper extremity interventions that focus on the hand.

## **3. Research Design and Methods**

This study will be a single blind randomized controlled trial. Subjects will be blinded to the purpose of the study. All outcome measures will be performed by a therapist blinded to group assignment. A controlled trial will be utilized to determine the additive effect of presenting rehabilitation activities in a virtual environment as compared to standard upper extremity exercise. We will randomize subjects to treatment and control groups using a computerized random number generator.

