### ***3.4 Subject Selection and Enrollment Considerations***

#### ***3.5.1 Inclusion Criteria***

- 1) healthy persons between the ages of 20 and 90
- 2) persons six weeks post stroke between the ages of 20 and 90
- 2) person with enough shoulder, elbow, wrist, and hand movement to actively interact with the video games

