### **5. Data Handling and Statistical Analysis**

All efforts will be made to keep subjects' personal information confidential. All subject names will be removed from the data and the data will be tagged using a coded ID number.

Demographic, clinical outcome and survey data will first be recorded on paper. All kinematic and computerized performance data will be collected on computer. These computer files will be identified by the coded subject ID number. All data will be transferred to an Excel spreadsheet with subjects identified by this same ID number. Spreadsheets will be stored on a drive that is password protected. Data will only be accessible to study staff and will be retained for seven years. The link between subject identity and subject ID number will be destroyed when data collection is completed.

Our primary outcome measures will be the WMFT (Aim 2) and the duration of motor activity (measure of compliance, Aim 1). The primary outcome measures and all secondary outcome measures described above will be subjected to a repeated measured analysis of variance, with between-group factors Therapy Type (Virtual Simulations (VS), Standard Exercise (SE)) and within-group factor Test (Before, Post, One Month retention, Six Months Retention). Our post-hoc analyses of the Therapy Type by Test interaction effects will focus on the Month 1 versus Month 6 comparison. We will be quantifying training effects by comparing group means as well as by percent change in performance, and by comparing the recovery curves obtained from Tests 1-4. All clinical outcomes used are well established measures of upper extremity functional recovery with published minimum clinically important differences which we will use to evaluate the significance of our findings.

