**Subjects:** This will be a randomized, blinded study. The same subjects will be utilized for all three aims. Upon IRB approval 30 persons with chronic strokes will be recruited from the outpatient rehabilitation department of JFK Medical Center, its hospital based fitness center program for persons with stroke and its stroke support group. **Inclusion criteria** are a) 25-85 years old, b) unilateral stroke, c) score of 24 or greater on the Folstein Mini-Mental Status Exam(52), d) Score of 1 or better on extinction and inattention portion of NIH Stroke Scale (NIHSS)(53), e) Fugl-Meyer (FM) between 30-60/66 (54), f) Score of 1 or better on language portion of NIHSS, g) intact cutaneous sensation (e.g. ability to detect <4.17N stimulation using Semmes-Weinstein nylon filaments(55). **Exclusion criteria are:** Orthopedic issues that would limit the ability to perform regular upper extremity activity. **Randomization:** Because level of impairment may affect (a) compliance with training regime, (b) intrinsic motivation, (c) adherence, and finally (d) measures of effectiveness, it is crucial (especially in a study with limited n) to balance the treatment and control arms. Because simple randomization of subjects to arms may not result in a balanced design, and because the ability to statistically adjust for baseline arm differences in these two characteristics is likely to be limited, we will use the following strategy to ensure arm equivalency. Subjects' initial scores on our measurement of motor control impairment caused by the stroke the (UEFMA) will be dichotomized into low/high. Subjects are then classified into the cell corresponding to their impairment level. Subjects in each cell (n1, n2) are provided random IDs (to prevent an ID by case recruitment association), and an investigator blinded to the randomization process then randomly assigns the first case in each cell to treatment or control arm. Each following subject within the cell is then assigned sequentially to the alternate arm. This is done for all cells to balance the source of variability between arms. **Blinding: Subjects** will be blinded to the purpose of the study and group assignment. They will also be blinded to their previous self-reported scores and their previous performance on objective tests. **Research assistants** performing outcomes measures will be blinded to group assignment and blinded to previous performance on all tests.

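### Time since stroke is left out of both the randomisation and the WMFT model, so differing recovery slopes would add avoidable error to the Aim 2 comparison

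*Protocol*

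**What the plan says.** **Who enters.** Protocol 3.5.1 admits "persons six weeks post stroke between the ages of 20 and 90". No upper limit is given. The words *at least* are absent, but six weeks is most sensibly read as a minimum. The Background says long-term training is "necessary for sub-acute and chronic patients to continuously improve their functional abilities"; that sentence is about access to therapy and does not define enrolment.

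**How long they are followed.** Under 3.1 subjects "train using one of the protocols for three to twelve months" and are retested one and six months after training.

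**How they are allocated.** Protocol Section 3: "We will randomize subjects to treatment and control groups using a computerized random number generator". No strata, blocks or minimisation are stated.

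**How they are analysed.** Section 5 specifies a repeated-measures ANOVA "with between-group factors Therapy Type (Virtual Simulations (VS), Standard Exercise (SE)) and within-group factor Test (Before, Post, One Month retention, Six Months Retention". There is no covariate.

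**What is said about heterogeneity.** Protocol 3.3 concedes that "by its nature stroke is an extremely variable condition", but the only control it names is screening on impairment.

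**The SAP.** Under Aim 1 (Subjects, Randomization), it departs from simple allocation: "Because simple randomization of subjects to arms may not result in a balanced design". Its remedy balances the arms on dichotomised upper-extremity Fugl-Meyer score only. It recruits 30 persons with chronic stroke, a term it does not define, and compares the motivation-enhanced games with unenhanced games. It has no standard-exercise arm.

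**The concern.** Aim 2 asks whether home virtual simulation (HBVS) improves on standard home exercise (HBSE), so it rests on change from before training. A subject who enters at six weeks, trains for three months and returns six months later is followed to roughly ten months after stroke. Arm function may improve over part of that period without any training. A subject who enters years after stroke may have a flatter course.

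If so, change scores differ between early and late entrants in both arms, for a reason unrelated to treatment. The Before test in the ANOVA absorbs differences in starting level. It does not absorb differences in slope, and slope is what the Therapy Type by Test interaction measures. At stake is the precision of the WMFT comparison, in a trial with 25 to 30 subjects per arm.

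**Working it through.** **Inputs from the protocol.** Power 0.80, alpha 0.05, effect size f = 0.3, correlation 0.1, 25 per group, 30 with allowance for attrition (all 3.3).

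**Inputs assumed.** The documents give neither the share of early subjects (p) nor their extra gain (D). I take p = 1/3 and D = 0.5, 1.0 and 1.5, where D is in units of the SD of change among subjects of similar time since stroke and is the same in both arms.

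**1. The plan's own figure.** For the between-groups test of a repeated-measures ANOVA with 2 groups and m = 2 occasions, lambda = f²·N·m / [1 + (m − 1)·rho] = 0.09 × 50 × 2 / 1.1 = 8.18 on 1 and 48 df. Power is 0.800, so 25 per group is reproduced. With three groups, as 3.3 words it, two occasions would need 21 per group.

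**2. Variance of change.** Leaving a two-class factor out of the model multiplies the variance by v = 1 + p(1 − p)D² = 1 + 0.222·D².

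**3. Power if the planned effect size excludes this variation.** A two-sided two-sample t test at 5% has 80% power at 25 per arm for d = 0.809. This d is solved back from 80% power and is not a protocol figure. With the inflation, d becomes 0.809/√v.

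| D | v | d/√v | Power, 25 per arm | Power, 30 per arm |
|---|---|---|---|---|
| 0 | 1.000 | 0.809 | 0.80 | 0.87 |
| 0.5 | 1.056 | 0.787 | 0.78 | 0.85 |
| 1.0 | 1.222 | 0.732 | 0.72 | 0.80 |
| 1.5 | 1.500 | 0.660 | 0.63 | 0.71 |

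The 30-per-arm column applies only if nobody is lost, since 3.3 reserves the extra subjects for attrition. A smaller early share matters less: p = 0.10 with D = 1 gives v = 1.09 and 77% power at 25 per arm.

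**4. Cross-check on the F test of step 1.** Dividing lambda by v gives 7.75, 6.69 and 5.45, and power of 0.78, 0.72 and 0.63. The two methods agree.

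**5. Power if the planned effect size already includes this variation.** The unadjusted analysis keeps its 0.80. Adjustment multiplies lambda by v and costs one df: lambda = 8.64, 10.00 and 12.27 on 1 and 47 df, with power of 0.82, 0.87 and 0.93.

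**6. Chance imbalance.** At 30 per arm, a 20-point difference means at least 6 more early subjects in one arm than in the other.
- With exactly 20 early among 60 and 30 drawn per arm (hypergeometric), the probability is 0.17.
- With two independent binomial arms at 1/3, it is 0.13.

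A 20-point imbalance shifts the group difference by 0.20·D = 0.10, 0.20 or 0.30 SD. The standard error of the unadjusted difference, √(2v/30), is 0.27, 0.29 or 0.32 SD, so that shift is less than one standard error in each case.

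**7. Imbalance and inflation are the same quantity.** With independent arms, the variance of the shift caused by imbalance is 2 × 0.222·D²/30 = 0.0148·D². The variance of the group difference is 2v/30 = 0.0667 + 0.0148·D². The imbalance term is exactly the inflation term, so the two must not be added.

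**The case against.** The strongest reply is that randomisation with a concurrent control already deals with natural recovery. A reader might infer from the mixed population that spontaneous recovery cannot be told apart from training gain, or that Aim 2 is biased. The documents do not support that. Section 3 specifies a randomised controlled trial with blinded assessors, Aim 2 is a between-group comparison, and recovery common to both arms cancels on average. What remains is precision.

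A reader might also count chance imbalance as a second harm on top of the inflated variance. Step 7 shows that it is the same sampling error.

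Third, the power loss is conditional. Protocol 3.3 does not say what variability lies behind f = 0.3, and it calls stroke highly variable, so the planned effect may already allow for this. In that case no planned power is lost, and adjustment is simply a gain forgone. Both p and D are assumptions as well, and 3.3 describes the trial as a pilot. All of this stands.

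Finally, the SAP enrols chronic stroke only. That does not settle the protocol's Aim 2, because the SAP compares two game groups and has no HBSE arm. It does conflict with protocol 3.5.1, and if only chronic stroke is enrolled, the concern is smaller.

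**Conclusion.** The point holds as a matter of efficiency and leaves the validity of the comparison intact. The protocol neither stratifies nor adjusts for time since stroke, although its entry criterion, read as a minimum, spans early and late subjects. With one third early and an extra gain of 0.5 to 1.5 SD in both arms, the variance of WMFT change rises by 6% to 50%. Nominal 80% power at 25 per arm becomes 78% to 63% if the planned effect size leaves this variation out. If it is included, power stays at 80% and adjustment lifts it to between 82% and 93%. Adjusting helps under either reading, and it costs so little that it should be done.

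A flat statement that the trial is underpowered for this reason would go too far. The documents fix neither the early share, nor the extra gain, nor the content of the planned effect size.

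**What to change.** 1. **Protocol Section 5.** Prespecify time since stroke at enrolment and its interaction with Test as covariate terms in the WMFT model and the other Aim 2 models. The interaction is needed: a main effect alone adjusts level and leaves the Therapy Type by Test error unchanged.
2. **Protocol Section 3, if randomisation has not started.** Stratify the computer-generated list by time since stroke, at a cut the sponsor chooses, with permuted blocks within strata. If randomisation is under way, make the first change alone, before any unblinded analysis.
3. **Eligibility.** State whether six weeks in 3.5.1 is a minimum, and reconcile that criterion with the SAP's chronic-stroke population.

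**Cost.** Protocol wording, a stratified list, and one or two degrees of freedom in any one comparison of change. The date of stroke is already needed to apply the inclusion criterion, so no new data or visits are required.

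### Protocol and SAP assign subjects by two different rules: one states no restriction, the other fixes about 28 of 30 assignments by alternation, and they must be replaced by one

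*Protocol*

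**What the plan says.** **Protocol, Section 3:** "We will randomize subjects to treatment and control groups using a computerized random number generator". That is the whole description. No ratio, block, stratum, number of arms or concealment step is given.

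**Protocol, Section 3.3:** "we will need a sample size of 25 subjects in each of the three groups", then an enrolment of 30 in each of two groups to allow for attrition. The same section adds: "Although we will screen for patients with homogeneous impairments, by its nature stroke is an extremely variable condition".

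**SAP, Aim 1, Subjects (Randomization):** "30 persons with chronic strokes will be recruited from the outpatient rehabilitation department". The section says impairment may affect compliance, motivation, adherence and effectiveness, and calls balance between arms crucial, especially when n is limited. It goes on: "Because simple randomization of subjects to arms may not result in a balanced design". Baseline scores ("UEFMA) will be dichotomized into low/high") define two cells, and no cut-off is given. An investigator "randomly assigns the first case in each cell to treatment or control arm", after which "Each following subject within the cell is then assigned sequentially to the alternate arm".

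Neither document mentions the other's rule.

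**The concern.** The allocation rule is what makes this a randomized comparison, and the two documents give different ones. Under the protocol a generator makes the assignments. Under the SAP, chance enters once per cell and the rest follow in turn. Staff cannot do both, and each rule has its own weakness.

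- **Protocol.** Nothing in the text secures equal groups or balance on the one factor the SAP singles out. Protocol eligibility (Sections 3.5.1 and 3.5.2) asks for enough movement to play and excludes severe weakness and severe tone, but sets no numeric impairment range. The SAP's Fugl-Meyer window of 30 to 60 out of 66 is narrower but still leaves wide variation.
- **SAP.** Strict alternation lets anyone who knows the last assignment in a cell foresee the next. Whoever decides when, or whether, to enrol a candidate could then influence which arm that person joins. This selection bias cannot be measured or removed afterwards.

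**Working it through.** **1. The plan's own group size.** Protocol Section 3.3 gives power 0.8, alpha 0.05, effect size 0.3 (read as Cohen's f, an assumption) and correlation 0.1. For the between-groups test in a repeated-measures ANOVA, the noncentrality is λ = f²·N·m / (1 + (m−1)ρ). With two groups and m = 2 measurements, N = 50 gives λ = 0.09 × 50 × 2 / 1.1 = 8.18 and power 0.800, so 25 per group reproduces. It does not reproduce with three groups (21 per group at m = 2) or with the four tests of Section 5 (16 per group for two groups, 13 for three). Going from 25 to 30 implies 1 − 25/30 = 16.7% attrition; no rate is stated. The target is therefore itself unsettled: three groups of 25, two of 30, or the SAP's 30 in total.

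**2. Group sizes if Section 3 means simple 1:1 randomization (assumption).** The size of one arm is Binomial(N, 0.5).

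| | N=60 | N=30 |
|---|---|---|
| Exactly equal, C(N, N/2)/2^N | 10.3% | 14.4% |
| Central 95% range of one arm | 22 to 38 | 10 to 20 |

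At N=60, both arms hold at least 25 in 84.5% of trials (sum of C(60,x)/2^60 over x = 25 to 35), so one arm is below 25 before attrition in 15.5%. With three arms and 90 subjects, 30/30/30 occurs in 0.9% and the smallest arm is below 25 in 32%.

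**3. What unequal sizes cost.** Efficiency relative to equal arms is 4·n₁·n₂/N².
- 25/35: 4 × 25 × 35 / 3600 = 97.2%
- 22/38: 4 × 22 × 38 / 3600 = 92.9%
- 10/20: 4 × 10 × 20 / 900 = 88.9%

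**4. Impairment balance under simple randomization.** Let h subjects be high on UEFMA, with a ~ Binomial(h, 0.5) of them and b ~ Binomial(N−h, 0.5) of the low subjects going to arm one. The imbalance is D = |a/(a+b) − (h−a)/(N−a−b)|. The table gives P(D ≥ 0.20). The lower figure lets each subject be high independently; the upper fixes h.

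| Share high (assumption) | N=30 | N=60 |
|---|---|---|
| 50% | 30-36% | 13-16% |
| 30% | 25-27% | about 10% |

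Equal arm sizes alone do not cure this. With unstratified equal arms and half the subjects high, the figure is 47% at N=30 and 20% at N=60, partly because a gap of exactly 20 points is an attainable value there. Strata are needed as well as blocks.

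**5. The SAP rule at N=30, two cells, all splits enumerated.** The arms differ by at most 1 within a cell and 2 in total (15/15 or 14/16). The share of high subjects differs by at most 6.7 points. The price is that 2 assignments are random and 30 − 2 = 28, or 93%, are fixed by the one before.

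**6. Number of arms.** Alternation between two arms gives no instruction for a third. Protocol Section 3.3 counts three groups and then two. Section 5 has virtual simulation against standard exercise. The SAP's Treatment Protocol puts both of its groups on the game system.

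**The case against.** A reader might infer that Section 3 prescribes unrestricted randomization. It does not say so. A random number generator can equally produce a blocked or stratified list, so the fair statement is that no restriction is specified. Steps 2 to 4 depend on the simple reading.

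A reader might also infer that the SAP rejects the protocol's method and supersedes it. The SAP says only that simple randomization may fail to balance the arms and that impairment may affect the outcomes. It never refers to the protocol's rule, and its worry is tied to a small n.

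Simple randomization is valid. Chance imbalance is already allowed for in the test's error rate and is not bias. UEFMA is measured before training and could be used as a covariate, even though the Aim 1 compliance outcome has no pre-training value. This stands, but Protocol Section 5 plans no such adjustment and the SAP expects adjustment to be of limited use.

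In defence of the SAP rule, it gives subjects random IDs within cells. If everyone in a cell were recruited before anyone was assigned, and the order followed those IDs, alternation would not be foreseeable. The SAP does not say that allocation waits for full recruitment, and its wording describes subjects following one another. Blinding the assigning investigator and the assessors does not stop recruiting staff from working out the sequence.

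What stands: the conflict itself, the lack of any stated safeguard in the protocol, and the predictability of the SAP rule.

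**Conclusion.** The concern holds in limited form. The two rules are incompatible and need to be replaced by one.

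On the assumption of simple randomization, the protocol's rule guarantees neither equal groups nor impairment balance. To say that it delivers neither would go too far, because both arms reach 25 at enrolment in 84.5% of two-arm trials of 60. Nor do the figures support a claim of serious power loss: a 25/35 split keeps 97% of the efficiency. Impairment imbalance is the larger issue, chiefly at the SAP's N=30, and its size depends on the assumed share of high scorers.

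The SAP's rule is not the benchmark to adopt. It secures balance, but with assignment in order of arrival about 28 of 30 allocations are predictable to anyone who knows the previous one. That is the more serious weakness, and the rule does not extend to three groups.

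**What to change.** Replace both the Section 3 sentence and the SAP's assignment rule with one rule, worded identically in each document:

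- a computer-generated list in permuted blocks of randomly varying size, concealed from those who recruit, test and treat;
- strata of low and high UEFMA at a numerical cut-off fixed before the first subject is randomized;
- each allocation released only after the subject's pre-test UEFMA score is recorded;
- the arms and the ratio stated, once Protocol Sections 3.3 and 5 and the SAP's Treatment Protocol agree on which groups are randomized.

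**Cost.** Rewording, a new list, and waiting for the UEFMA score before release. UEFMA is already taken before training, so no subjects, visits or measurements are added. Balance is slightly looser than under alternation: with two arms and a largest block of 4 (an illustration), an unfinished block can leave a difference of 2 per stratum, so 4 over two strata, against 2 under the SAP rule. Settling which arms exist is a separate decision that has to come first.
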